10.0 ADVERSE EVENTS

10.1 Adverse Event

According to ICH guidelines (Federal Register. 1997; 62(90):25691-25709) and 21 CFR 312.32, IND Safety Reports, and ICH E2A, Definitions and Standards for Expedited Reporting, an adverse event is defined as follows:

An adverse event is any untoward medical occurrence in a clinical investigation subject administered a medicinal product and which does not necessarily have a causal relationship with this treatment. An AE can therefore be any unfavorable and unintended sign (including an abnormal laboratory finding), symptom, or disease temporally associated with the use of a medicinal product, whether or not considered related to the medicinal product.

Medical conditions present at screening (i.e., before the study treatment is administered) are not adverse events and should not be recorded on adverse event pages of the CRFs. These medical conditions should be adequately documented on the subject chart. However, medical conditions present at baseline that worsen in intensity or frequency during the treatment or post-treatment periods should be reported and recorded as adverse events.

10.2 Serious Adverse Event

An adverse event should be classified as an SAE if it meets one of the following criteria:

Fatal	Adverse event results in death.
Life threatening:	The adverse events placed the subject at immediate risk of death. This classification did not apply to an adverse event that hypothetically might cause death if it were more severe.
Hospitalization:	It required or prolonged inpatient hospitalization. Hospitalizations for elective medical or surgical procedures or treatments planned before enrollment in the treatment plan or routine check-ups are not SAEs by this criterion. Admission to a palliative unit or hospice care facility is not considered to be a hospitalization.
Disabling/incapacitating	Resulted in a substantial and permanent disruption of the subject's ability to carry out normal life functions.
Medically significant:	The adverse event did not meet any of the above criteria, but could have jeopardized the subject and might have required medical or surgical intervention to prevent one of the outcomes listed above.

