3.3.3 Safety Endpoints

1. Serious adverse events and total adverse events attributable to the exercise intervention will be reported.

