4.2 Safety Measures

Individuals will be instructed to stop exercise and contact their doctor if they have any of the following symptoms during exercise or after an exercise session:

- Disorientation, dizziness, blurred vision or fainting
- Sudden onset of nausea, vomiting
- Unusual or sudden shortness of breath
- Irregular heartbeat, palpitations, chest pain
- Leg/calf pain, bone pain, unusual joint pain or pain not caused by injury
- Muscle cramps or sudden onset of muscular weakness or fatigue

The most common risks of exercise include fatigue and muscle soreness, and possibly joint or skeletal injury. These risks are reduced by proper warm-up/cool down periods, conservative and individual exercise prescriptions and progression, and careful education about ways to reduce injury by an experienced exercise physiologist. Musculoskeletal injuries will be assessed by one of the study clinicians. Individuals with a suspected serious musculoskeletal injury as a result of exercise will be instructed to be evaluated by their personal physician or to be evaluated at urgent care or the emergency department. Subsequent exercise will either be held to allow for recovery, or modified, depending on the nature of the injury and physician assessment. If a medical issue develops which is not related to exercise, the exercise prescription will also be modified as needed.

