7.5 Duration of Follow-Up

Refer to section 8.0 for the evaluations to be done at baseline, during the 24 week intervention, and at the 24 week time point. After the end-of-study visit, there will be no further study assessments or follow-up. Participants who are randomized to the control arm will be offered the delayed exercise intervention after 24 weeks (which will include a one-on-one session with the exercise physiologist and weekly telephone support), but this intervention is optional, and in addition, there will not be any other assessments or clinic visits.

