15.8 Institutional Review Board/Ethics Committee

The PI will assure that an appropriately constituted IRB/EC that complies with the requirements of 21 CFR Section 56 or written assurance of compliance with ICH (E6) guidelines will be responsible for the initial and continuing review and approval of the clinical study. Before initiation of the study, the PI or designee will forward copies of the protocol and Consent Form to be used for the study to the IRB/EC for its review and approval. The PI or designee will also assure that all changes in the research activity and all unanticipated problems involving risks to human subjects or others will be reported promptly to the IRB/EC, and that no changes will be made to the protocol without prior Sponsor and IRB/EC approval, except where necessary to eliminate apparent immediate hazards to human subjects.

The PI or designee must promptly notify the IRB/EC of any SAE occurring at the site and of any safety reports (e.g., IND Safety Reports) received from the Sponsor, or its designee.

The Investigator or designee will be responsible for submitting periodic progress reports to the IRB/EC at intervals appropriate to the degree of subject risk involved in the study, but not less than once per year and at the completion or termination of the study.

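### The disability criterion for a serious adverse event requires permanence, so a substantially disabling but temporary exercise injury treated without admission can be left out of the SAE output

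*Combined protocol and SAP*

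**What the plan says.** Section 10.2 lists five criteria and states: "An adverse event should be classified as an SAE if it meets one of the following criteria". Any one is enough. The disabling row applies if the event "Resulted in a substantial and permanent disruption" of the participant's normal functioning. The hospitalization row is met if "It required or prolonged inpatient hospitalization". The last row, for medically significant events, applies when none of the others is met. It needs two things together: the event could have put the participant in jeopardy, and it might have called for treatment to avert an outcome in the earlier rows.

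Section 10.4 monitors adverse events for 24 weeks from baseline in the exercise arm, and for 48 weeks in controls who take up the delayed programme. Section 7.5 adds: "After the end-of-study visit, there will be no further study assessments or follow-up". Under section 15.8 the investigator or a designee "must promptly notify the IRB/EC of any SAE occurring at the site".

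Section 4.2 names the expected harms: "The most common risks of exercise include fatigue and muscle soreness, and possibly joint or skeletal injury". It directs a participant with a suspected serious musculoskeletal injury to her own physician, urgent care or the emergency department. Section 3.3.3 defines the safety endpoint: "Serious adverse events and total adverse events attributable to the exercise intervention will be reported".

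**The concern.** The harm most specific to this intervention is musculoskeletal injury. Such an injury can stop a participant walking or working for weeks, be managed entirely as an outpatient, and then heal. In ordinary terms that is a substantial disability. Under section 10.2 it fails the disability criterion because it is not permanent, and it may fail every other criterion too.

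What is at stake is the SAE output, one of the two safety outputs in section 3.3.3, and the prompt notice that SAE status triggers under section 15.8. Safety is a stated objective (section 3.1.3), the protocol has no stopping rules (section 4.1), and few SAEs are expected. Classifying one or two events differently could decide whether the report says that there were none.

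**Working it through.** The plan states no figure on this point. The check is a reading of the criteria against one another, followed by two short calculations.

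**Step 1. Apply each criterion in section 10.2 to one case.** Take an exercise injury that substantially limits walking for several weeks, is treated without admission, is expected to heal, and threatens nothing worse.

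| Criterion | Met? | Reason |
|---|---|---|
| Fatal | No | No death |
| Life-threatening | No | No immediate risk of death |
| Hospitalization | No | Inpatient admission is required; section 4.2 allows outpatient and emergency department evaluation |
| Disabling | No | Substantial but not permanent |
| Medically significant | Not clearly | Needs possible jeopardy and a possible need for treatment to avert an earlier outcome; for disability, that outcome is the permanent one |

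This case can fall outside all five rows. If treatment might have been needed to prevent admission or permanent loss of function, and the event could have put the participant in jeopardy, the last row can apply and there is no gap.

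**Step 2. How long can an injury be watched?** Weeks of observation left = end of surveillance − week of onset. In the exercise arm the end is week 24 (section 10.4).

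- Onset at week 4: 24 − 4 = 20 weeks
- Onset at week 8: 24 − 8 = 16 weeks
- Onset at week 12: 24 − 12 = 12 weeks
- Onset at week 20: 24 − 20 = 4 weeks
- Onset at week 24: 24 − 24 = 0 weeks

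If onset is uniform over weeks 0 to 24 (an assumption), the mean is 24 / 2 = 12 weeks. The sample progression in section 7.2 reaches 150 minutes per week at week 8, so an injury at that level has at most 16 weeks of observation. For controls on the delayed programme the same pattern runs over weeks 24 to 48, so no exposed participant has more than 24 weeks from the start of exercise. Section 10.4 asks for a stop date and an outcome but gives no rule for an event still unresolved when surveillance ends.

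**Step 3. What could a few events do to the report?** The documents give no rate for such injuries. Assume 0 to 2 among the 49 participants planned for the exercise arm (section 13.4). This range is an illustration, not an estimate. Exact (Clopper-Pearson) 95% limits for x events in n = 49 are the 2.5% point of Beta(x, n − x + 1) and the 97.5% point of Beta(x + 1, n − x). For x = 0 the lower limit is 0 and the upper is 1 − 0.025^(1/49) = 7.3%.

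| SAEs | Rate | Exact 95% limits |
|---|---|---|
| 0 | 0% | 0 to 7.3% |
| 1 | 1/49 = 2.0% | 0.05 to 10.9% |
| 2 | 2/49 = 4.1% | 0.5 to 14.0% |

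If these were the only SAEs in the arm, leaving them out would change a reported 2.0% or 4.1% to 0%. If there were none, nothing would change.

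**The case against.** The strongest reply is that much of the ground is already covered.

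- **Permanence can be judged without later follow-up.** Section 10.4 has the investigator or a designee assess every adverse event and try to reach a diagnosis, and some diagnoses settle the question at once. A reader might infer that a 24-week trial cannot establish permanence at all. The documents do not support that: nothing in section 10.2 requires permanence to be shown by later observation. What stands is that it will often be uncertain, and that a temporary disability fails the criterion however well it is judged.
- **The medically significant row is broad.** Its wording is hypothetical, and its listed outcomes include admission as well as permanent disability. It plausibly catches many of the more serious skeletal injuries. A reader might infer that disabling injuries treated without admission generally escape SAE status. That goes too far: the gap is confined to those that threaten no listed outcome.
- **The event does not vanish.** All adverse events are recorded with relatedness, action taken and outcome (section 10.4) and graded by CTCAE (section 10.5). An injury attributed to exercise enters the attributable total in section 3.3.3. A reader might infer that the harm would go unreported; the documents show only that it would be missing from the SAE count.
- **SAE status is not the only route to the IRB.** Section 10.8.2 refers to reporting events under IRB policy, and section 15.8 separately requires prompt notice of unanticipated problems involving risk. This weakens the point about notice but does not remove it.
- **The size is unknown.** This stands in full. The limits in step 3 only restate assumed counts, and they leave out controls who take the delayed programme.

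None of these replies covers the temporary, substantially disabling, non-admitted injury with no threat of a listed outcome.

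**Conclusion.** The point holds in a narrow form. Followed as written, section 10.2 can class as non-serious an exercise injury that is substantially disabling but temporary, is treated without admission, and threatens neither death, life, admission nor permanent disability. Such an injury would be left out of the SAE output, although it would be recorded and graded as an adverse event and, if attributed to exercise, counted in the attributable total.

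The number of such events is unknown and may be zero. The conclusion rests on the wording of the criteria and on injury being a harm that the protocol itself names; it does not depend on the illustrative counts. No efficacy, power or sample-size figure is affected. It is a modest correction, worth making because it concerns how this intervention's own expected harm is classified.

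**What to change.** In the disabling row of section 10.2, drop the permanence condition and keep the threshold of substance: the event must cause a substantial disruption, whether or not permanent, with the rest of the row unchanged. The medically significant row refers back to the earlier outcomes and would then take on the same standard.

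The requirement of substance should stay. A looser wording that accepted disruption that is either substantial or persistent would bring in minor but lasting complaints. That matters here because section 5.2.4 does not exclude participants with lymphedema or peripheral neuropathy.

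The cost is one line of protocol wording, a few more SAE forms, and an SAE count that may be slightly higher. No extra follow-up visit is needed.

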10.3 Unexpected Adverse Event

An unexpected adverse event is defined as an event that has a nature or severity, or frequency that is not consistent with a moderate exercise program, or the prior medical condition of the subject or other treatment given to the subject.

“Unexpected,” as used in this definition, refers to an adverse experience that has not been previously observed and reported in preclinical or clinical studies.

10.4 Monitoring and Recording Adverse Events

Participants will be monitored for AEs throughout their study surveillance period (24 weeks from baseline for participants in the intervention arm, 48 weeks from baseline for control participants who opt to complete the delayed intervention). The occurrence of an AE may come to the attention of study personnel during the weekly phone interview by the exercise interventionist, by UW study staff personnel conducting telephone reminders for surveys or biospecimen collection, or by a study participant calling the study team. If an SAE comes to the attention of study personnel, the research team at UW will complete an AE form. All AEs will be assessed by the investigator or qualified designee and recorded in the CRFs. The investigator should attempt to establish a diagnosis of the event on the basis of signs, symptoms and/or other clinical information. In such cases, the diagnosis should be documented as the adverse event and/or serious adverse event and not described as the individual signs or symptoms. The following information should be recorded:

- Description of the adverse event using concise medical terminology
- Description as to whether or not the adverse event is serious, noting all criteria that apply
- The start date (date of adverse event onset)

Protocol 10045

- The stop date (date of adverse event resolution)
- The severity (grade) of the adverse event
- A description of the potential relatedness of the adverse event to study intervention, a study procedure, or other causality
- The action taken due to the adverse event
- The outcome of the adverse event

10.5 Grading Adverse Event Severity

All AEs will be graded in severity according to the NCI Common Terminology Criteria for Adverse Events (CTCAE) Version 4.0. If a CTCAE criterion does not exist, the investigator should use the grade or adjectives: Grade 1 (mild), Grade 2 (moderate), Grade 3 (severe), Grade 4 (life-threatening), or Grade 5 (fatal) to describe the maximum intensity of the adverse event.

10.6 Attribution of an Adverse Event

Association or relatedness to the study agent will be assessed by the investigator as follows:

- **Definite:** The event follows a reasonable temporal sequence from exposure to the exercise intervention, has been previously described in association with the intervention, and cannot reasonably be attributed to other factors such as the subject's clinical state, other therapeutic interventions or concomitant medications; AND the event disappears or improves with discontinuation of the exercise intervention and/or reappears on re-initiating the exercise intervention..
- **Probable:** The event follows a reasonable temporal sequence from exposure to the exercise intervention and has been previously been described in association with the exercise intervention OR cannot reasonably be attributed to other factors such as the subject's clinical state, other therapeutic interventions or concomitant medications.
- **Possible:** The event follows a reasonable temporal sequence from exposure to the exercise intervention, but could be attributable to other factors such as the subject's clinical state, other therapeutic interventions or concomitant medications.
- **Unlikely:** Toxicity is doubtfully related to the exercise intervention. The event may be attributable to other factors such as the subject's clinical state, other therapeutic interventions or concomitant medications.
- **Unrelated:** The event is clearly related to other factors such as the subject's clinical state, other therapeutic interventions or concomitant medications.

For general AE assessment, an AE is considered related if it is assessed as definitely, probably, or possibly related; unrelated if it is assessed as unlikely related or unrelated.

10.7 Adverse Event Recording Period

AEs will be monitored and recorded in study-specific case report forms (CRFs) from the time of first exposure to the exercise intervention. AEs with an onset date prior to the first exposure to the exercise intervention will not be recorded, except in the case of clinically significant worsening of the AE during the specified AE monitoring time frame.

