3.1.3 Safety Objectives

1. To evaluate the safety of the moderate exercise intervention.

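### Sections 10.7 and 10.4 conflict on recording control-arm adverse events before week 24, and the safety endpoint in 3.3.3 makes no use of the randomised control arm

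*Combined protocol and SAP*

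**What the plan says.** The safety objective in 3.1.3 is "To evaluate the safety of the moderate exercise intervention". The matching endpoint in 3.3.3 reads "Serious adverse events and total adverse events attributable to the exercise intervention will be reported". Section 13 contains no safety analysis by arm.

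Two sections set the recording period.

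- Section 10.7: "AEs will be monitored and recorded in study-specific case report forms (CRFs) from the time of first exposure to the exercise intervention". It continues that "AEs with an onset date prior to the first exposure to the exercise intervention will not be recorded", with an exception for clinically significant worsening during the monitoring time frame.
- Section 10.4: surveillance lasts 24 weeks from baseline in the intervention arm and "48 weeks from baseline for control participants who opt to complete the delayed intervention". It gives no period for controls who decline. It also says that all AEs are recorded in the CRFs, and that an AE form is completed if a serious event reaches staff.

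Under 7.2 and 7.5, controls are offered the program after their week-24 assessments, and taking it up is optional.

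According to 10.4, events may come to light "during the weekly phone interview by the exercise interventionist, by UW study staff personnel conducting telephone reminders for surveys or biospecimen collection", or when a participant calls the study team. Under 10.6, "an AE is considered related if it is assessed as definitely, probably, or possibly related".

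**The concern.** A control is first exposed to exercise after week 24 or never. Read literally, 10.7 therefore keeps control events from the randomised period out of the CRFs, while 10.4 points the other way without covering every control. Staff who learn of a non-serious control event at week 10 have no consistent instruction.

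This matters because background events are expected. Participants are one to six months past chemotherapy, may be on maintenance therapy, and may stay on study after recurrence (5.1.3, 9.0). Section 7.6 itself plans for anaemia, neutropenia, fever and low platelets. Attribution does not remove this background. The 'possible' category applies when "The event follows a reasonable temporal sequence from exposure to the exercise intervention, but could be attributable to other factors", and it counts as related. The investigator must judge relatedness without a concurrent control rate, although the trial has a randomised comparator that could supply one. Non-serious events not captured at the time are unlikely to be recoverable at analysis.

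**Working it through.** The plan gives no safety rate or safety sample size to reproduce. The arm size does reproduce: 78 / (1 - 0.20) = 97.5, rounded up to 98, or 49 per arm (13.3, 13.4).

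**Step 1. Apply each rule to a control event with onset in weeks 0-24.**

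| Control | Under 10.7 | Under 10.4 |
|---|---|---|
| Later takes up the program | Not recorded, unless it worsens in the monitoring period | Within the stated 48 weeks from baseline |
| Declines the program | Not recorded; exposure never occurs | No period stated |
| Serious event known to staff | Same exclusion on its face | AE form completed; IRB notice under 15.8 |

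The rows disagree, and neither column gives a complete rule for all 49 controls. The worsening exception cannot supply a control rate, because it captures only events that worsen in the monitoring period.

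The week-24 blood draw is a concrete case. Section 2.7 lists its risks, and 10.4 asks for relatedness to a study procedure. For a control, the draw precedes any exposure to exercise, so 10.7 excludes a resulting event that 10.4 wants classified.

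**Step 2. Time affected if 10.7 prevails.** Control time in the randomised period is 49 x 24 = 1,176 participant-weeks, ignoring dropout, with routine AE recording in none of it. The exercise arm has at most 49 x 24 = 1,176 recorded weeks, less dropout and any gap between randomisation and first exposure.

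**Step 3. Would repairing 10.7 give the endpoint a control figure?** No. The related categories in 10.6 (definite, probable, possible) all require a temporal sequence from exposure to exercise. An unexposed control cannot have an attributable event, so the 3.3.3 count of attributable AEs is exercise-only whatever the recording period. This is a separate defect with its own repair.

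**Step 4. Ascertainment.** The weekly call in 7.2 asks about fatigue, soreness, injury and other symptoms. That is 24 planned contacts per exercise participant before week 24, and none per control. Controls are heard through reminder calls or their own call. Both arms complete questionnaires at weeks 12 and 24 (8.1), so matched contacts already exist.

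**Step 5. Precision of a repaired comparison.** The half-width of the 95% interval for a risk difference, with equal risk p in both arms, is 1.96 x sqrt(2p(1-p)/n). The plan gives no AE rate, so p is an assumption.

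| p (assumed) | n = 49 per arm | n = 39 per arm |
|---|---|---|
| 10% | 0.119 | 0.133 |
| 20% | 0.158 | 0.178 |
| 40% | 0.194 | 0.217 |

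The 39 is the planned number of completers per arm (78 / 2).

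**The case against.** The strongest reply is that the protocol never promised a between-arm safety comparison: 3.3.3 asks for attributable events, section 13 adds nothing, and 4.1 argues that moderate exercise carries little risk. That stands as a limit on severity. It does not reconcile 10.7 with 10.4, and the attributable wording is itself part of the point.

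A reader might infer that no control event will be recorded before week 24. The documents do not support that as a flat statement, since it requires 10.7 to override 10.4. Section 10.4 counts from baseline, says that all AEs are recorded, and names reminder calls that controls also receive. Because staff cannot know before week 24 who will take up the program, its likelier working reading is that all controls are followed from baseline, with an extension for those who opt in. For the same reason, a reader should not infer that control risk would be estimated only from those who opt in. That would mean discarding the decliners' records, which 10.4 does not say.

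Nor do the documents support a claim that control serious events vanish. Those that staff learn of should produce an AE form (10.4) and prompt IRB notice (15.8). Both arms also complete fatigue, pain and side-effect items at baseline and weeks 12 and 24. These allow some randomised comparison of tolerability, but they do not record injuries, grades or other AEs.

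**Conclusion.** The point holds in two parts. First, 10.7 and 10.4 give conflicting rules for control events in weeks 0-24, and non-serious events have no consistent one. Second, and independently, 3.3.3 counts attributable events only, so the plan does not use its randomised control arm to judge background events. It would be wrong to say that 10.7 alone removes the control figure, because correcting 10.7 would leave the second part untouched.

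The size is conditional. If 10.7 governs, up to 1,176 control participant-weeks have no routine AE recording. If 10.4 governs, the gap is the unstated period for decliners, and the plan gives no uptake rate from which to size it. The documents also give no event or attribution rates, so no numerical bias in the safety result can be stated. The primary efficacy endpoints are unaffected. The change should be made, because it concerns a stated objective and is cheap to put right.

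**What to change.** 1. In 10.1, 10.4 and 10.7, set one period: record AEs and SAEs from randomisation to the week-24 assessment for every randomised participant in both arms. Define pre-existing conditions as those present before randomisation; 10.1 now uses the start of study treatment. For controls who take up the delayed program, continue to week 48 and report that period separately.
2. In 3.3.3, add a descriptive table by randomised arm of SAEs and all AEs in weeks 0-24, regardless of attribution, with the risk difference and 95% CI. Keep the attributable count as an exercise-only line.
3. Add the same short AE question to the week-12 and week-24 questionnaires in both arms, and base the comparison of non-serious events on those contacts. List events known only from the weekly calls separately.
4. Restrict the by-arm comparison of non-serious events to participants in both arms randomised after the amendment. Alternatively, for each matched contact, use participants in both arms who reached it after the amendment. Dropping earlier controls alone would break the concurrent randomised comparison.

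The cost is an IRB amendment, edits to four short sections, one question on existing questionnaires, and AE forms for controls. No visits are added. Earlier participants are not covered. The comparison is coarse: about 12 to 19 points either side at 49 per arm for assumed risks of 10% to 40%, and wider if fewer are covered. It could show a large excess, but could not establish that the arms are equally safe.
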